Subjects: Subjects from the age of 16 years with documented diagnosis of asthma and/or COPD, daily treated with dry powder inhaler (DPI) or metered dose inhaler (MDI), or both, will be invited to voluntarily participate. Exclusion criteria is age <16 years, no access to use BankID or similar electronic personal identification service, not using smartphone of type Android or iPhone, plan to stop use DPI and/or MDI the following 6-12 weeks from inclusion. No able to independently handle and inhale through DPI or MDI device.

Total sample size: Eighty subjects (females and males) with daily treatment for COPD or asthma will be sufficient, based on the assumption of 25% percentage improvement in success rate of correct

inhalation technique in the interventional group compared with control group (75% versus 50%) with 80% power at 5% significance level, including dropouts at 6-12 weeks follow-up visit.

Intervention: At the baseline visit patients will be randomised to app-based intervention consisting of education and training of inhalation technique of all inhalers used on daily basis (the inhalation app-module). Stratified randomisation based on type of inhaler(s); MDI, DPI or both MDI and DPI will be applied. The intervention is the inhalation app-module, which is a medical device that is embedded the AsthmaTuner app. The AsthmaTuner app is a CE-marked cloud-based system, provided by MediTuner AB in Stockholm, Sweden. The intervention group will be instructed to use the inhalation app-module on daily basis to improve their inhalation technique.

Control group: Standard education of inhalation technique using list of standardised criteria and non-app-based education of inhaler technique.

Endpoints: Primary endpoint is the rate of subjects with successful inhalation techniques based on subjective critical endpoints (CIP Table 2) and the following objective endpoints at the 6-12 weeks follow up visit:

- DPI: PIF \geq 30 L/Min, time to PIF <0.5 seconds measured with the investigational device.
- MDI: inspiration time (> 3 seconds) and PIF less than 60 L/Min measured with the investigational device.

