A.6 Design of the clinical investigation

A.6.1 General

This confirmatory multicentre two-armed stratified randomised controlled blinded study analysing the effect of app-based education and training of inhalation technique compared with control group on subjective critical and objective endpoints of inhalation technique at 6-12 weeks follow-up visit. The study approach is intention to treat, including 80 subjects with daily therapy of DPI and/or MDI for asthma and/or COPD, Figure 2.

[figure not shown]

Figure 1 Two-armed, parallel-designed, individual single-blinded stratified randomised controlled trial.

The subjects will be randomly assigned to one of the following two arms (1:1):

1. Standard assessment and correction together with app-based education and training at baseline visit and at least every week or whenever needed during the following study period of 6-12 weeks.
2. Standard assessment and instructions on inhalation technique at baseline visit according to Table 2.

Table 2. Subjective assessment of handling and inhalation techniques, adopted from Aksu F. et al. [8]. If all criteria are not deemed to correction per inhaler, including objective endpoints defines primary endpoint of subject with successful inhalation technique.

	DPI	MDI
1	Shook inhaler (critical for Easyhaler)	Shook the inhaler (critical for suspension)
2	Removed the cap of the inhaler correctly (critical)	Removed the cap of the inhaler correctly (critical)
3	Actuated one dose / loaded capsule correctly (critical)	Breathed out before slow inhalation
4	Inhaler kept in upright position (critical for some inhalers)	Breathed out and away from the mouthpiece of the inhaler
5	Breathed out and away from the mouthpiece of the inhaler	Placed the inhaler mouthpiece correctly in mouth
6	Inhaler correctly placed in mouth. Inhaled with lips sealed around the mouthpiece (critical)	Inhalation slow before or immediately when dose fired (critical)
7	Inhaled forcefully through the mouth after firing dose (critical)	Inhaled through the mouth after dose fired (critical)
8	Inhaled without interruption (critical)	Inhaler was correctly placed in mouth during the entire inhalation (critical)
9	Breath-holding more than 5 seconds after inhalation	Inhaled without interruption (critical)
10	Breathed out and away from the mouthpiece of the inhaler	Breath-holding more than 5 seconds after inhalation

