11	For Handyhaler or similar, check powder drug rests in capsule, if necessary, inhale again	Breathed out and away from the mouthpiece of the inhaler

Each subject in both intervention and control arm will receive standard assessment and instruction on inhalation technique according to criteria in Table 2 at baseline visit. The study endpoints will be collected at the follow-up visit (6-12 weeks).

Randomisation and masking

Each of the 80 subjects is stratified to block of 4 numbers according daily used inhaler of (1) DPI, (2) MDI or (3) both MDI/DPI. Simple randomisation (1 to 1) will be applied in each block and at each study site. The randomisation will be blinded for the evaluator at 6-12 week visit, which practically means that not the same study personnel will do the baseline randomisation and the final 6-12 weeks assessment of inhalation technique.

Endpoints

Primary endpoint is number of subjects presenting successful inhalation techniques as defined by objective endpoints divided by:

- DPI: PIF \geq 30 L/Min, time to PIF <0.5 seconds measured with the investigational device.
- MDI: inspiration time (> 3 seconds) and PIF less than 60 L/Min measured with the investigational device.
- Together with subjective critical endpoints at 6–12-week follow-up visit, assessed by study personnel, Table 2.

Secondary endpoints:

- Feasibility and safety of using the investigational device for education and training of inhalation technique based on questionnaire and interviews from subjects and healthcare personnel, Appendix 3.

Study personnel will get access and be trained in methods and procedures for informed consent, randomisation, investigational device, data collection and documentation. The study endpoints will be documented in electronic Case Report Form (CRF) provided by Karolinska Institutet. Data analysis will start as soon as all 80 included subjects have completed or considered to be lost to follow-up at 6-12 week's visit by local investigator.

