To ensure optimal lung deposition of inhaled medication the inspiratory flow rate (PIF) could be assessed by manual meters. The CE-marked manual meter device In-Check Dial has the benefit that the inhaling resistance can be adjusted to certain inhalers. The device is limited to only measuring PIF and provides no other type of education and training of inhalation technique. This pragmatic RCT-study will allow use of manual meters in the control group if this is part of standard care at any of the investigational sites.

A.6.3 Subjects

Inclusion criteria

Subjects, age ≥ 16 years, willing to voluntarily participate in the study and give electronic written informed consent through BankID or similar service, with daily inhalation therapy through DPI and/or MDI for doctor's diagnosed asthma or COPD.

Exclusion criteria

Age < 16 years, no access to use BankID nor use of smartphone of type Android or iPhone, plan to stop use treatment with DPI and/or MDI the following 6-12 weeks. Medical condition affecting the ability to independently inhale or use DPI or MDI device(s).

The total time for study participation is estimated to 40 min, 20 min per visit, over a period of 6-12 weeks. Severe asthma or COPD exacerbation or the severity of airway obstruction will affect inhalation technique, therefore, subjects will receive information to treat exacerbation and contact their healthcare provider in case of exacerbation. The study coordinator and medical doctor [name] take individual decision if study subject should stop to use the medical device or due to medical condition unable to be treated with an inhaler. Although stopping the study is not expected, this can be done if on background of unexpected device deficiency, the decision will be taken by study coordinator and principal investigator [name].

The ethical principal of this study is that subjects who wants to use the interventional device after study termination can do that when the device is CE-marked, as long as they are managed for asthma or COPD at any of the investigational sites or other healthcare provider who offers AsthmaTuner. Additionally, subjects will be informed at the time of study enrolment they are free to discontinue the study at any point, without any particular reason.

Lost to follow-up

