Informed consent	X	
Randomization	X	
Questionnaires of medical history and usability	X	X
Spirometry test	X	
Standard review and correction of inhalation technique	X	X
Objective assessment of inhalation technique		X
Adverse events or device deficiency		X

Randomisation

Computer-based randomisation stratified for subjects' daily inhaler use into three groups of DPI, MDI or both DPI and MDI devices of four block numbers in each stratum per investigational site.

Interview and electronic questionnaires

- A structured health questionnaire completed at the first visit will provide information regarding medical history, health care utilization and experiences of inhalation education and training, Appendix 4.

Dynamic spirometry

- The lung function test will measure forced expiratory flow in one second (FEV₁), forced vital capacity (FVC), and FEV₁/FVC according standardised procedures [31]. Applied percent of predicted reference values, adjusting for age, sex, height, weight and ethnicity, will be calculated based on continuous prediction equations of normal population [32].

Standard review of inhalation technique

- All subject's ability to handle their inhaler(s) and inhalation technique will be reviewed and corrected at baseline visit and assessed at 6–12-week follow-up visit according to endpoints in Table 2.

Investigational device - app-based intervention for education and training of inhalation technique

1. Subjects randomised to intervention will receive instructions on using the investigational device, accompanied with written information (instructions for use) from study personnel at baseline visit. The subjects are instructed to use the investigational device 3-7 times per week to achieve the maximal effect.

2. Instruction for use manual on how to use medical investigational device will be available for subjects and study personnel at investigational sites (Appendix 5). Briefly, subjects follow the following procedure:
 - a. Baseline visit: Download (Apple Store or Google Play) and login with BankID or similar to the AsthmaTuner app. Automatic Bluetooth connection will be established between the MIR AsthmaTuner and the app.
 - b. Study personnel at Karolinska institutet set up login through BankID or SITHS card to AsthmaTuner Careportal for study personnel at investigational site.
 - c. Enter patient information: Fill out patient's initial letters, study ID, height, weight and type of inhaler. Press "next" to start the test.

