 - d. The visual representations and explanatory text illustrating the step-by-step procedures within the app are displayed in Figure 3a-c, including the AsthmaTuner spirometer and the adjustable resistance and app-illustrations of training module of inhalation technique with DPI or MDI.

[figure not shown]

Figure 3a: Illustrations showing how to enter the app-based medical device in the CE-marked device AsthmaTuner.

[figure not shown]
[figure not shown]

[figure not shown]
Figure 3b: Illustrations showing how to prepare for an inhalation test in the app-based medical device and the MIR AsthmaTuner spirometer with the adjustable resistance from 0 to 5 for measuring inspiratory flows.

Follow the instructions to practice your inhalation technique.

Follow the instructions to practice your inhalation technique.

Failed inhalation test:

Successful inhalation test:

[figure not shown]

Figure 3c: Illustrations of failed and successful inhalation test with DPI and MDI inhalers from the app-based medical device.

While subjects enter the CE-marked “AsthmaTuner application”, subjects are presented with the option to enter the investigational device by selecting the “Practice now” button. It will be made clear to the subjects that they enter a non-CE marked part of the otherwise CE marked device. It will also be clear that the inhalation app-module is an investigational device only to be used in clinical study setting. Subjects are directed to the inhalation tool, which comprises educational resources and training materials for inhalation techniques. The tool is divided into four chapters: *Asthma quiz*, *COPD quiz*, *Prepare your inhaler*, and *Inhalation technique*. Education and preparation materials are specifically tailored to the inhalers included in the patient's treatment plan. The “Inhalation technique” chapter features a video demonstration and detailed instructions on preparing the spirometer prior to training sessions. Automated feedback is provided to subjects based on objective criteria for each selected inhaler, determining whether their inhalation technique meets the required standards. Subjects are encouraged to successfully training inhalation three times per session.

Follow-up visit 6-12 weeks

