The subjective assessment of inhalation will be conducted ‘blinded’ by study personnel. The assessment will be filmed through Teams or Zoom to facilitate standardised review and judgment of inhalation technique according to Table 2. The film is stored on local hard disk of the computer and will be deleted after the “blinded” assessment is done.

The objective assessment will be performed in both groups according to Figure 3 a-c. Data is stored in the AsthmaTuner cloud.

Compromising factors that might affect the outcomes are i.e. ongoing exacerbation (asthma or COPD), the follow-up visit can therefore be rescheduled within the time frame of 6-12 weeks in case of any medical condition is deemed to affect the study endpoints. The coordinating investigator will

take the decision to withdraw subject in case of any not resolved medical condition, not present at baseline visit, is judged to significantly affect inhalation technique or subject's safety at the follow-up visit.

A.6.5 Monitoring plan

Before the beginning of the investigation, the Sponsor will appoint an independent monitor at Karolinska Trial Alliance (KTA). Monitoring will be performed before, during the study and after the study is completed in accordance with the ISO 14155 GCP (Good Clinical Practice) standard. Study conductance, source data, device accountability, adherence to the study protocol, Good Clinical Practice, and regulatory requirements will be monitored.

Data to be monitored at site are e.g.

- Patient information and Informed Consent. That each patient included in the study has signed an Informed Consent and that no study procedures have begun before the date of the consent.
- That inclusion criteria are met for the included patients
- That all types of adverse events and serious adverse events, device related or not, as well as, those that might have led to SAE shall be reported, and even if those are listed as expected in this Clinical Investigation Plan.
- Check that all CRF data are entered
- Other CRF data will be source data verified against patient records according to a detailed Monitoring Plan (that will contain details regarding the overall monitoring) signed by the Sponsor prior to the start of the study. At least 10% of the patients will have data in the CRFs 100% source data verified.

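### The objective half of the primary endpoint is scored on the app's own inhalation test, which only the app arm is described as practising, so part of any gain may be familiarity with the test

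*Protocol*

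**What the plan says.** - **Endpoint (A.6.1, Endpoints).** A success needs the Table 2 critical items plus objective limits. For MDI these are "MDI: inspiration time (> 3 seconds) and PIF less than 60 L/Min measured with the investigational device". For DPI they are PIF of at least 30 L/min and time to PIF below 0.5 s, read the same way.
- **Follow-up visit (A.6.4).** Table 2 is filmed and judged blinded. For the flow part, "The objective assessment will be performed in both groups according to Figure 3 a-c". The captions identify Figure 3 as the app module's procedure: entering the module, preparing the test with the spirometer and adjustable resistance, and failed and successful results.
- **App arm (A.6.4).** Subjects randomised to intervention are instructed on the device and told to use it 3-7 times a week, with three successful inhalations encouraged per session. "Automated feedback is provided to subjects based on objective criteria for each selected inhaler, determining whether their inhalation technique meets the required standards".
- **Control arm.** The synopsis (A.1.5) gives "Standard education of inhalation technique using list of standardised criteria and non-app-based education of inhaler technique"; A.6.1 gives "Standard assessment and instructions on inhalation technique at baseline visit according to Table 2". The comparator text (A.6.2) "will allow use of manual meters in the control group if this is part of standard care", and says of the meter it names: "The device is limited to only measuring PIF and provides no other type of education and training of inhalation technique".
- **Schedule (A.6.4, Table 3).** The row "Objective assessment of inhalation technique" is marked at follow-up only.

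**The concern.** The measuring instrument for half of the primary endpoint is also the training instrument of one arm. By follow-up the app arm has repeated the scored manoeuvre on that equipment for weeks and has been told each time whether it passed. A control, as described, meets the equipment for the first time when being scored.

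The superiority claim in A.5 is about inhalation technique, not about handling a spirometer fitted with a resistance simulator. A control who inhales well but fails an unfamiliar first attempt counts as a primary failure, whatever the Table 2 result, because both parts are required. This error runs in one direction only. Analysis cannot remove it, because A.6.2 itself says that standard assessment cannot measure these flow quantities precisely. The trial is described as confirmatory and is meant to support CE marking, so it should be able to answer whether controls simply failed an unfamiliar test.

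**Working it through.** **Step 1. Exposure to the scored test before it is scored**

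| | App arm | Control arm |
|---|---|---|
| Instruction on the device | yes, baseline (A.6.4) | none described |
| Practice with the app test | 3-7 times a week for 6-12 weeks (A.6.4) | none described; education is non-app-based (A.1.5) |
| Pass/fail feedback on flow | automated (A.6.4) | none described |
| Other flow measurement | not needed | manual meter where it is standard care; PIF only (A.6.2) |
| Objective assessment scheduled | follow-up only (Table 3) | follow-up only (Table 3) |

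A manual meter cannot rehearse time to PIF or inspiration time, which are also scored. Baseline spirometry is listed with FEV₁, FVC and their ratio only, which are expiratory measures.

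**Step 2. Size: illustration only.** The protocol gives no figure for a familiarity effect.

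Inputs from the protocol:
- 80 subjects, 1:1 allocation, 20% dropout: 80 × 0.8 / 2 = 32 per arm.
- Control success 50% and planned difference 25 points (A.1.5, A.7).
- 5% significance level, taken here as two-sided.

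Assumptions with no source in the protocol:
- True success is 50% in both arms.
- A fraction f of otherwise successful controls fails through unfamiliarity.

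Formulas:
- Otherwise successful controls: 32 × 0.50 = 16; affected: 16f.
- Control rate: 0.50(1 − f); shift: 50f points.
- Apparent risk ratio: 0.50 / [0.50(1 − f)] = 1/(1 − f).
- Chance of significance: exact binomial enumeration of the pooled chi-square test without continuity correction. This stands in for the planned logistic regression.

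| f | Controls affected | Shift (points) | Share of planned 25 | Apparent RR | Significant, 32/arm | of which favouring app | Significant, 40/arm (no dropout) |
|---|---|---|---|---|---|---|---|
| 0 | 0 | 0 | 0% | 1.00 | 6.0% | 3.0% | 5.7% |
| 5% | 0.8 | 2.5 | 10% | 1.05 | 6.5% | 4.6% | 6.3% |
| 10% | 1.6 | 5 | 20% | 1.11 | 8.0% | 6.9% | 8.1% |
| 20% | 3.2 | 10 | 40% | 1.25 | 14.2% | 13.9% | 15.7% |
| 30% | 4.8 | 15 | 60% | 1.43 | 24.7% | 24.7% | 28.6% |
| 40% | 6.4 | 20 | 80% | 1.67 | 39.2% | 39.2% | 45.8% |

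**Step 3. Cross-check with a different model.** Let composite success be s × o, where s is the Table 2 pass rate and o the objective pass rate, assumed independent. Fix the control composite at 50% and let familiarity add g points to o in the app arm. The composite then rises by s × g. For s from 60% to 90%:
- g = 5: 0.6 × 5 to 0.9 × 5 = 3.0 to 4.5 points.
- g = 10: 6.0 to 9.0 points.
- g = 15: 9.0 to 13.5 points, which is 36-54% of the planned 25.

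By the normal approximation at 32 per arm, the chance of a significant result favouring the app is about 4-6%, 7-11% and 11-19% for the three values of g, against a nominal 2.5%. The Table 2 requirement dilutes the artefact but does not remove it.

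**The case against.** The strongest reply is that practising this manoeuvre *is* the intervention. The limits are physical flow quantities at a resistance matched to the inhaler, and a trained patient should do better on them. Much of that stands: most of any gain may be the intended skill, and nothing in the protocol shows that a separate familiarity component exists or how large it is. But handling the spirometer and Airflow Trainer is not the target skill, and a short orientation given to everyone leaves a trained skill in place.

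Other points:
- **Unseen material.** Figure 3, Appendix 5 and the CRF are not available here and may set attempt or display rules. This stands, so the fix is conditional on it. Figure 3b does cover preparing the test, but preparation steps are not practice.
- **Wording that is not arm-specific.** A.1.1 and A.1.5 describe the app download, A.6.2 the supply of equipment, and A.6.3 the return of the device, all without naming an arm. The per-protocol rule in A.7 counts inhalation tests without limiting itself to the app arm. This leaves some doubt, but no text describes controls using the test before follow-up.
- **Blinded Table 2 items.** These include forceful, slow and uninterrupted inhalation, so skill at the app test alone cannot produce a success. That limits the concern to one component. It does not rescue a control who fails the flow test.
- **Smaller contrast.** Unscored manoeuvres give controls a little device practice just before scoring and may shrink a genuine difference somewhat. This is a real cost of unknown size.

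**Conclusion.** The concern holds. As described, the two arms reach the scored flow test with very different prior exposure to it, and the resulting bias, if any, can only favour the app. Its size cannot be established from the protocol. In the illustration it is small if 5-10% of otherwise successful controls are affected (2.5-5 points; 6.5-8.0% chance of significance against 6.0%) and material from about 20% (10 points; 14.2%). Those figures assume no true effect, 50% success, 32 per arm, and a fraction f with no source in the protocol. The conclusion also rests on reading the control arm as not using the app test before follow-up, and on the unseen figures and appendices not already equalising exposure. Confidence is medium. The change is worth making because it is cheap, acts on the primary endpoint and cannot be replaced by analysis afterwards.

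**What to change.** In A.6.4 (Follow-up visit), unless the figures or appendices already provide it:

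1. Complete the filmed Table 2 assessment first, so that the device test cannot influence it.
2. Give every subject in both arms the same standard orientation and the same fixed number of unscored manoeuvres on the spirometer with Airflow Trainer, without coaching on pass or fail. Three would match the number encouraged per training session.
3. Score a fixed number of attempts by one rule set in advance and applied identically in both arms.
4. Keep pass/fail feedback from the subject during unscored and scored attempts where this needs no software change, for example by turning the screen away.

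In A.7, add a supportive table of success by arm, separately for the objective limits and for the blinded Table 2 critical items. State that it shows where a difference arises but cannot by itself separate a real flow gain from test familiarity.

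Cost: a few minutes per follow-up visit on equipment already in use, and one table of data already collected. The module stays as tested (A.2.C). The downside is a possibly slightly smaller contrast between arms.
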